#### 8.1.2.1 Secondary Immunogenicity Endpoints

Humoral immune response of the aQIVc formulations in comparison with the QIVc vaccine in terms of HI antibody response against homologous vaccine strains:

- GMT: Geometric mean of HI antibodies at Day 181.
- GMFI: The Geometric mean of the fold increase in serum HI titer post-vaccination (Day 181) compared to pre-vaccination (Day 1).
- Percentages of subjects with HI titers  $\geq$ 1:40 on Day 181.

Derived variables:

- The GMT ratio (aQIVc formulation/QIVc) for each strain.
- The inter-group difference in the percentage of subjects with HI titer ≥1:40 (aQIVc formulation minus QIVc) for each strain.

Confidential

Effective Date: See System Metadata

In addition, the humoral immune response of the aQIVc formulations in comparison with the QIVc vaccine in terms of MN antibody response against homologous vaccine strains:

- GMT: Geometric mean of MN antibodies at Days 1, 29 and 181.
- GMFI: The Geometric mean of the fold increase in serum MN titer post-vaccination (Day 29 and Day 181) compared to pre-vaccination (Day 1).
- Percentages of subjects with seroconversion (defined as ≥ 4-fold increase for subjects with pre-vaccination MN titers ≥ Lower Limit of Quantitation (LLOQ) or as ≥ 4LLOQ for subjects with pre-vaccination MN titer <LLOQ) at Day 29.

Derived variables:

- The GMT ratio (aQIVc formulation/QIVc) for each strain
- The inter-group difference in the SCRs (aQIVc formulation minus QIVc) for each strain.

#### 8.1.2.2 Secondary Safety Endpoints

- SAEs, MAAEs, AEs leading to withdrawal or AESIs as collected during the study (Day 1 to End of Study).
- Solicited adverse events as evaluated by the investigator.

#### 8.1.3 Exploratory Endpoints

Exploratory endpoints that may be assessed in the study include the immunogenicity endpoints as measured on Day 29 by HI or MN assay using cell-derived target viruses or cell-derived heterologous target viruses. Details will be described in the Statistical Analysis Plan.

The results of these exploratory analyses may be presented in an addendum to the Clinical Study Report (CSR).

# 8.2 Success Criteria

This study is a Phase 2 study to explore the immunogenicity of different formulations of aQIVc versus QIVc. Although no success criteria are pre-specified, 95% confidence interval bounds will be used for statistical comparisons.

# 8.3 Analysis Sets

#### 8.3.1 All Enrolled Set

All screened subjects who provide informed consent, receive a subject ID and provide demographic and/or baseline screening assessments, regardless of the subject's treatment status in the study.

#### 8.3.2 All Exposed Set

All subjects in the All Enrolled Set who are randomized and received study vaccination.

#### 8.3.3 Safety Set

Subjects will be analyzed as "treated" (i.e., according to the vaccine a subject received, rather than the vaccine to which the subject may have been randomized).

#### **Solicited Safety Set**

All subjects in the Exposed Set with any solicited adverse event data including body temperature measurements or use of analgesics/antipyretics.

#### Unsolicited Safety Set (unsolicited adverse events)

All subjects in the Exposed Set for whom safety has been assessed after vaccination (including 30-minute post-vaccination assessment).

#### **Overall Safety Set**

All subjects who are in the Solicited Safety Set and/or in the Unsolicited Safety Set.

#### 8.3.4 Full Analysis Set (FAS) Immunogenicity

#### Full Analysis Set Immunogenicity

All subjects in the All Enrolled Set who are randomized, received study vaccination and provided immunogenicity data on Day 1 and Day 29 assessment.

In case of vaccination error, subjects in the FAS sets will be analyzed "as-treated" (i.e., according to the vaccine the subject actually received).

#### 8.3.5 Per Protocol Set (PPS) Immunogenicity

All subjects in the FAS Immunogenicity who:

- Correctly receive the vaccine (i.e., receive the vaccine to which the subject is randomized within the defined window).
- Have no protocol deviations leading to exclusion (see Section 8.3.8, Protocol Deviations) as defined prior to unblinding / analysis.
- Are not excluded due to other reasons defined prior to unblinding or analysis, including subjects who withdrew informed consent prior to Day 28.

#### 8.3.6 Other Analysis Sets

Other applicable analysis sets will be described in the SAP.

#### 8.3.7 Subgroups

Primary and secondary analyses of immunogenicity and safety endpoints will be done for the total population and by age subgroup (50 - 64 years and  $\ge 65$  years).

Additional subgroup analysis will be conducted for previous vaccination history, sex and comorbidity risk score (below 50 and above 50). Refer to the SAP for further details.

#### 8.3.8 Protocol Deviations

A protocol deviation is any change, divergence, or departure from the study design or procedures of a study protocol. A protocol deviation may be a reason to remove data from an analysis set at the time of analysis. CSR-reportable protocol deviations will be defined as exclusionary from the analysis according to protocol objectives and endpoints, which will be specified in the statistical analysis plan. In some cases, exclusion of data may be due to a reason other than a protocol deviation, e.g. early termination.

#### 8.4 Statistical Analysis Plan

#### 8.4.1 Analysis of Demographic and Baseline Characteristics

Descriptive statistics (mean, standard deviation, median, minimum and maximum) for age, height, weight, BMI and comorbidity risk score at enrolment will be calculated overall and by vaccine group.

Distributions of subjects by sex, race and ethnic origin, prior vaccination status and country will be summarized overall and by vaccine group.

Demographic and baseline characteristics will also be presented by the age subgroup.

#### 8.4.2 Analysis of Primary Objectives

#### 8.4.2.1 Analysis of Primary Safety Objectives

The primary objective is to assess the safety using the solicited local and systemic adverse events (AEs) for 7 days following vaccination (Day 1 through Day 7), reported severe solicited local or systemic AEs for 7 days following vaccination (Day 1 through Day 7), reported unsolicited adverse events for 28 days following vaccination ((Day 1 to Day 29), and reported SAEs, MAAEs and AESIs for 28 days after vaccination (Day 1 to Day 29).

#### 8.4.2.1.1 Statistical Hypothesis

No statistical hypothesis testing will be performed for the safety objectives.

#### 8.4.2.1.2 Analysis Sets

All safety objectives will be evaluated based on the Solicited Safety Set and Unsolicited Safety Set.

#### 8.4.2.1.3 Statistical Methods

The statistical analyses of all safety endpoints will be descriptive in nature. Percentage of subjects will be presented by group for the overall age group as well as by age subgroup.

A logistic regression analysis will be applied with the binary response (presence of solicited adverse reaction or no reaction as reported by the subject), to explore the relation with antigen and MF59 levels as factors as well as with age and previous vaccination history. This model will be applied for both reported solicited local or systemic adverse events (AEs) for 7 days following vaccination and reported severe solicited local or systemic AEs for 7 days following vaccination (Day 1 through Day 7).

#### 8.4.2.2 Analysis of Primary Immunogenicity Objectives

The primary objective is to assess the immunogenicity assessed using the HI or MN assay at Day 29.

#### 8.4.2.2.1 Statistical Hypothesis

No formal statistical hypothesis testing will be performed for the immunogenicity objectives.

#### 8.4.2.2.2 Analysis Sets

All immunogenicity objectives will be evaluated based on the PPS Immunogenicity. In the case that there is >5% difference in the total number of subjects between the PPS and the FAS Immunogenicity, additional analysis based on the FAS Immunogenicity will be conducted.

#### 8.4.2.2.3 Statistical Methods

All statistical analyses for HI (and MN) titers will be performed on the logarithmically (base 10) transformed values. Individual HI titers below the detection limit (<10) will be set to half of that limit (5); values above the upper limit of quantification will be set to the upper limit.

Reverse cumulative distribution curves of HI and MN titers will be presented graphically by time-point and strain.

Unadjusted estimates for GMTs, GMFIs and pertaining 2-sided 95% CIs will be calculated assuming a log-normal distribution of the titers and will be completed by providing minimum, maximum and median titers for each vaccine group. Binary data (i.e., percentages of subjects with seroconversion and with titer  $\geq$  1:40) will be summarized for each group and

will be reported together with 2-sided 95% CIs calculated according to Clopper Pearson's method.

For immunogenicity data, it may be reasonable to consider missing immunogenicity values as missing completely at random (MCAR), i.e., not informative. Therefore, the immunogenicity analysis will comprise a complete case analysis only, without introducing any bias.

The analysis model for the HI GMT will be done using a general linear model on logtransformed (base 10) Day 29 titers as the outcome variable, with antigen levels and MF59 levels as factors, and age subgroup, previous vaccination history and log10 pre-vaccination titer as covariates. From this model, adjusted differences in the least square means (on the log scale) between the adjuvanted vaccine arms and the non-adjuvanted arm will be produced with 95% confidence limits. The estimated difference and the confidence limits will be backtransformed to obtain an adjusted GMT ratio (each aQIVc formulation versus QIVc) with 95% confidence limits. Each of the four strains will be analyzed separately. In addition, unadjusted GMT ratios for each aQIVc formulation versus QIVc will be presented.

Interaction effects between the antigen and MF59 factors will be explored. Other models may be investigated. In addition, adjusted GMT ratios will be calculated using formulation as categorical factor in this general linear model.

A similar model as described above will be used for the GMFI on Day 29 excluding the prevaccination titer as covariate.

The binary endpoints (i.e. seroconversion or titer  $\geq$ 1:40) at Day 29 from each aQIVc formulation versus QIVc will be compared using the Miettinen and Nurminen method without adjustment for the age stratum. Each of the four strains will be analyzed separately. Additional exploratory analysis will be done including antigen and MF59 levels and adjustment for age and previous vaccination history using a generalized linear model for binary data.

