## **Statistical Analyses:**

The primary analysis will be conducted on the immunogenicity and safety data collected up to Day 29.

All HI and MN titers below the lower limit of detection (i.e.,  $\leq$  LLOQ) will be set to half that limit (i.e.,  $\frac{1}{2}$  \* LLOQ). A general linear model (GLM) will be fitted with logarithmically transformed (base 10) antibody titer as the response variable, with antigen levels and MF59 levels as factors, and age subgroup, previous vaccination history and log10 pre-vaccination titer as covariates. Geometric mean titers and the associated CIs will

Name of Sponsor:	Protocol	Generic name of study vaccines:
Seqirus Ltd UK	number:	Investigational MF59-adjuvanted Quadrivalent
	V201_01	Subunit Inactivated Cell-derived Influenza
		Vaccine (aQIVc)
		Quadrivalent Subunit Inactivated Cell-derived
		Influenza Vaccine (QIVc)

be calculated by exponentiation (base 10) of the least square means of the logarithmically transformed (base 10) antibody titer. From the model, an adjusted difference in the least square means (on the log scale) will be produced with 95% confidence limits. The estimated difference and the confidence limits will be back-transformed to obtain an adjusted GMT ratio (each aQIVc formulation versus QIVc) with 95% confidence limits. Each of the four strains will be analyzed separately.

The statistical analysis of the Geometric Mean Fold Increase (GMFI) in (HI or MN) GMTs post-vaccination (Day 29) compared to pre-vaccination (Day 1) will be conducted using the same model described above excluding the pre-vaccination titer as a co-variate.

The difference in seroconversion rates (SCRs) or percentage of subjects with HI titer  $\geq$ 1:40 at Day 29 from each aQIVc formulation versus QIVc will be presented with 95% CIs using the Miettinen and Nurminen method without adjustment for the age stratum. Each of the four strains will be analyzed separately. Additional exploratory analysis will be done including antigen and MF59 levels and adjustment for age and previous vaccination history using a generalized model for binary data.

The statistical analyses of all safety endpoints will be descriptive in nature. Percentage of subjects will be presented by vaccine group for the overall age group as well as by age subgroup.

Additional details on the statistical analysis can be found in Section 8 Statistical Considerations.

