## 8.1.1.1 Primary Immunogenicity Endpoints

Humoral immune response of the aQIVc formulations in comparison with the QIVc vaccine in terms of HI antibody response against homologous vaccine strains:

- Geometric Mean Titer (GMT): Geometric mean of HI antibodies at Day 1 and Day 29.
- Geometric Mean Fold Increase (GMFI): The Geometric mean of the fold increase in serum HI titer post-vaccination (Day 29) compared to pre-vaccination (Day 1).
- Percentages of subjects with HI titers  $\geq$  1:40 at Day 1 and Day 29.
- Percentage of subjects with seroconversion (defined as a ≥4-fold increase in titer postvaccination in those with pre-vaccination titer above the LLOQ (1:10), or a postvaccination titer ≥1:40 for subjects with baseline titer below the LLOQ (1:10) for HI antibodies at Day 29).

Note that the HI assay could be replaced by the MN assay due to a lack of agglutination.

Derived variables at Day 29:

- The GMT ratio (aQIVc formulation/QIVc) for each strain.
- The inter-group difference in the SCRs (aQIVc formulation minus QIVc) for each strain.

• The inter-group difference in the percentage of subjects with HI titer ≥1:40 (aQIVc formulation minus QIVc) for each strain.

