# **Geometric Mean Fold Increase**

Summary statistics (geometric mean, 95% confidence interval of GMT, minimum, median, maximum) of the relative increase in titers will be presented by assessment (Day 29), strain and vaccine group.

The analysis model for the fold increase in titers will be done using the same models as mentioned above on log-transformed (base 10) (Day 29 titers/Day 1 titers) as the outcome variable but excluding the log-transformed pre-vaccination titer.

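### Should the Day 29 GMFI model also adjust for the pre-vaccination titer?

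*Protocol*

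**What the plan says.** Protocol 8.4.2.2.3 fits a general linear model to the log10 Day 29 titer, with "age subgroup, previous vaccination history and log10 pre-vaccination titer as covariates". It then turns to the fold increase: "A similar model as described above will be used for the GMFI on Day 29 excluding the prevaccination titer as covariate". The protocol synopsis says the same ("same model described above excluding the pre-vaccination titer as a co-variate"). SAP 11.2 takes log10 of the Day 29 to Day 1 ratio as the outcome and fits the GMT models to it, "but excluding the log-transformed pre-vaccination titer". Age subgroup and previous vaccination history stay in the model.

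Protocol 8.1.1.1 lists GMFI among the primary immunogenicity endpoints. Its between-group variables are "The GMT ratio (aQIVc formulation/QIVc) for each strain", the difference in seroconversion rates and the difference in the share with titer at or above 1:40. It lists no GMFI ratio. Protocol 8.4.2.2.1 rules out formal testing. Protocol 8.2 sets no success criterion but says that 95% confidence bounds will be used for comparisons. The power statements in protocol 8.5 and SAP 5 concern the GMT ratio only.

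**The concern.** The log10 fold increase is the Day 29 value minus the Day 1 value. Leaving Day 1 out of the model fixes its slope on Day 29 at exactly 1. If the true slope is lower, because people with high titers rise less, the change score over-corrects. The group contrast is then noisier than it needs to be and moves with any chance difference in baseline titer.

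The baseline is available for every subject in the immunogenicity sets and is already in the GMT model, so the omission looks like precision given away for nothing on a primary endpoint. The same method carries over to Day 181 and to the MN assay. Two primary endpoints built from the same pair of titers could also order the formulations differently only because one model lacks a covariate, and this study feeds the choice of formulation for Phase 3.

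**Working it through.** **Inputs from the documents.** Day 29 SD s1 = 0.7 on the log10 scale, 95 evaluable per group, two-sided 0.05 (protocol 8.5, SAP 5). **Assumed, because neither document gives them:** baseline SD s0 = 0.5 to 0.7 and pre-post correlation r = 0.3 to 0.7.

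**1. The plan's own figures.** The standard error of a difference is 0.7 × √(2/95) = 0.1016. The ratio detectable with 80% power is 10^((1.960 + 0.842) × 0.1016) = 1.93, as stated. Two-sample t-test power with 188 degrees of freedom reproduces all ten cells of the power table, for example 83.86% at a true ratio of 2.0.

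**2. Variance of the two contrasts.**

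- Change score: s0² + s1² − 2·r·s0·s1
- Baseline-adjusted: s1²·(1 − r²)
- Difference: (s0 − r·s1)², which is never negative and is zero only when the slope r·s1/s0 equals 1.

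Example with s0 = 0.7, r = 0.5: the change score gives 0.49 + 0.49 − 0.49 = 0.490; adjusted gives 0.49 × 0.75 = 0.3675; the ratio is 1.33.

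| s0 | r = 0.3 | r = 0.5 | r = 0.7 |
|---|---|---|---|
| 0.7 | 1.54 | 1.33 | 1.18 |
| 0.6 | 1.34 | 1.17 | 1.05 |
| 0.5 | 1.19 | 1.06 | 1.00 |

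In the top row 95 subjects carry the information of 95/1.54 = 62, 95/1.33 = 71 and 95/1.18 = 81. By the normal approximation, power at a true ratio of 2.0 for change score against adjusted is then 70.7% against 87.4%, 84.2% against 92.8%, and 96.9% against 98.6%. A weaker correlation widens the gap: at s0 = 0.7 and r = 0.2 the variance ratio is 1.67.

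**3. Chance baseline imbalance.** With s0 = 0.7, one standard error of baseline difference is 0.1016 log10. At slope 0.5 the GMFI ratio moves by 10^(−0.5 × 0.1016) = 0.89, or by 1.12 in the other direction; two standard errors give 0.79. These are upper-end values, because the model keeps age subgroup and vaccination history, and only imbalance within those strata is left.

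**4. What the extra covariate would produce.** Write y0 and y1 for the log10 titers and X for all other terms. The GMT model is

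y1 = Xβ + γ·y0 + e.

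Subtract y0 from both sides:

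y1 − y0 = Xβ + (γ − 1)·y0 + e.

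The residuals, the group coefficients β and their standard errors are the same. Only the slope changes, from γ to γ − 1. This holds whether X has the eight groups or the antigen and MF59 levels. The same subjects enter both models, since the analysis sets require Day 1 and Day 29 data. A numerical check on simulated data with eight arms of 95 gave differences of about 10⁻¹⁵ in the coefficients and 10⁻¹⁷ in the standard errors. Baseline-adjusted GMFIs per group would be the adjusted GMTs divided by one common constant, the overall baseline GMT.

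**5. Is the change score poor against the plan's own yardstick?** Its variance is no larger than the 0.7² used for sample size when r ≥ s0/(2·s1): 0.50, 0.43 and 0.36 for s0 = 0.7, 0.6 and 0.5. Above those correlations the GMFI contrast is at least as precise as the comparison on which the power table rests.

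**The case for a change.** The strongest case is that the GMFI model exists to compare groups. Unadjusted GMFIs with intervals are planned anyway, so group or dose contrasts are what the model adds. Confidence bounds will be used for comparisons, and neither document says which result governs if the GMFI and GMT contrasts disagree. Seven formulations and four strains give 28 contrasts. About 28 × 0.317 = 9 of them would be expected to have a baseline difference beyond one standard error. QIVc is the shared comparator, so an imbalance in that arm moves all seven ratios for a strain together.

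The arithmetic stands, and the two contrasts can differ. The consequence does not follow. An imbalance in QIVc multiplies all seven ratios by the same factor and leaves their order unchanged. An imbalance between formulation arms could change the order on GMFI, but neither document has a ranking rule, and the adjusted GMT ratio on the same subjects corrects for it. The list in protocol 8.1.1.1 and the sample-size section already show which titer contrast carries the comparison. Making the two agree by adding the covariate would add no evidence, because the agreement would hold by construction. A sentence naming the GMT ratio as the lead comparison would do no harm, but it would only spell out what those sections imply.

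**Conclusion.** The concern is right about the statistics and needs no action. The GMFI contrast is at best as precise as the adjusted GMT ratio: its variance is 1.00 to 1.54 times as large for baseline SD 0.5 to 0.7 and correlation 0.3 to 0.7, both assumed. It can shift by about 11 to 12% for a one-standard-error baseline imbalance at equal SDs and correlation 0.5, before allowing for the two stratification factors that stay in the model.

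Against that, the remedy returns a result already planned, with the same estimates and the same standard errors. No bias is removed on average, since randomization makes the change-score contrast unbiased. No test, success criterion or power figure depends on it. The exclusion is stated the same way in the synopsis, protocol 8.4.2.2.3 and SAP 11.2, so it is a consistent modelling choice. It also keeps GMFI as a measure distinct from the adjusted GMT. The conclusion would differ only if a GMFI ratio were made a decision criterion, and neither document does that.

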#### 5.1.4 Randomization

Enrolled subjects will be randomized to one of the eight treatment groups in equal ratios (Groups A-H, see Table 3-1). Subjects will be stratified based on age ( $\geq$ 50 to 64 years and  $\geq$ 65 years) before being randomized. History of any influenza vaccination within 3 previous influenza seasons (yes/no) is also a stratification factor that will be applied to all subjects.

The subject will be randomized in the IRT/ Randomization and Trial Supply Management (RTSM) system. The subject will receive a unique Subject ID that will be used for all eCRFs and associated study documentation for the duration of the study. After randomization, the Screening Number ceases to be used and remains in the Screening and Enrolment Log only. The list of randomization assignments is produced by the IRT service provider and approved by the Sponsor according to the applicable Sponsor's Standard Operating Procedure (SOP).

If for any reason, after signing the ICF, the subject who is eligible and enrolled fails to be randomized, this is called a randomization failure and the early termination study procedures must be applied. The reason for all randomization failures should be recorded in the Screening and Enrolment Log and in the source document. The information on subjects who are randomization failures should be kept distinct from subjects who are screen failures, as described in Section 5.1.2, Screening.

If for any reason, after randomization the subject fails to undergo treatment, the subject has to be discontinued, and the reason should be recorded on the End of Study eCRF. The information on discontinued subjects should be kept distinct in the source documentation from randomization failures.

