### 8. GENERAL ISSUES FOR STATISTICAL ANALYSES

### 8.1 Adjustment for Covariates

The log-transformed antibody titers at Day 29 and Day 181 will be analyzed using an Analysis of Covariance (ANCOVA) model which includes the log-transformed pre-vaccination antibody titer, age subgroup stratification ( $\geq$ 50 – 64,  $\geq$ 65 years) and previous vaccination history stratification (no in previous 3 years, yes). Summary tables will show both adjusted and unadjusted GMTs for each vaccine group and adjusted and unadjusted GMT ratio for the different aQIVc investigational vaccines versus QIVc vaccine.

Instead of Vaccine group as categorical variable, levels of antigen and the amount of MF-59 will be included as covariates to model the antibody titers at Day 29 as function of the level of antigen and the amount of MF-59.

The main analysis of binary immunogenicity endpoints ((i.e., percentages of subjects with seroconversion and with titer  $\geq$ 1:40) will not be adjusted for any of the covariates. Binary data will be summarized for each group using unadjusted estimates and will be reported together with two-sided exact 95% CIs. Additional adjusted analysis may be done including the stratification factors age and previous vaccination history as covariates in a generalized linear model.

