### 8.3 Multicenter Studies

Stratification is used on two important factors related to the immunogenicity endpoints: age and previous vaccination history. These factors will be included in the statistical model. Centers will not be included in the statistical analysis, but countries will be considered in the sub-group analyses.

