### Analysis of binary endpoints

The number and proportion of subjects achieving the binary endpoints (seroconversion or HI titer >=1:40) will be summarized by assessment (Day 29), strain and vaccine group.

For each of the influenza vaccine strains and for each of the vaccine groups, summaries will include the associated two-sided 95% confidence intervals according to Clopper-Pearson.

The binary endpoints (i.e. seroconversion or titer  $\geq$ 1:40) will be compared between each aQIVc formulation and QIVc using the Miettinen and Nurminen method without adjustment for the age subgroup. The results will be presented as the difference in the percentage of subjects with 95% confidence intervals.

Additional supportive analyses may be done using generalized linear models with factors for vaccine group, age subgroup, pre-vaccination titer as well as previous vaccination history. Adjusted differences between vaccine groups with 2-sided 95% CI will be calculated based on the model and potential interaction effects will be examined.

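### The main seroconversion and HI ≥1:40 comparisons ignore the randomisation strata, and the SAP makes the protocol's adjusted analysis optional

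*Protocol*

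**What the plan says.** **Strata.** Protocol 5.1.4 stratifies the randomisation by age (50–64, ≥65 years) and adds: "History of any influenza vaccination within 3 previous influenza seasons (yes/no) is also a stratification factor that will be applied to all subjects". SAP 8.3 explains: "Stratification is used on two important factors related to the immunogenicity endpoints: age and previous vaccination history". It then says that these factors will enter the statistical model. The GMT models in Protocol 8.4.2.2.3 and SAP 11.2 do include both.

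**Main binary comparison.** Under Protocol 8.4.2.2.3 the binary endpoints at Day 29 "will be compared using the Miettinen and Nurminen method without adjustment for the age stratum". SAP 11.2 repeats this, "using the Miettinen and Nurminen method without adjustment for the age subgroup". SAP 8.1 is broader: the main binary analysis "will not be adjusted for any of the covariates", so vaccination history is left out as well as age. Protocol 8.4.3.2 carries the same method to the secondary immunogenicity endpoints.

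**Adjusted binary analysis.** There are three descriptions.
- Protocol 8.4.2.2.3 commits to it: "Additional exploratory analysis will be done including antigen and MF59 levels and adjustment for age and previous vaccination history", in a generalized linear model.
- SAP 8.1 makes it optional: "Additional adjusted analysis may be done including the stratification factors age and previous vaccination history as covariates".
- SAP 11.2 makes it optional with another set of terms: "Additional supportive analyses may be done using generalized linear models with factors for vaccine group, age subgroup, pre-vaccination titer", plus vaccination history. Only this version says that adjusted differences between vaccine groups will be calculated.

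SAP 16, which lists departures from the protocol, does not mention the change.

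**The concern.** Stratified randomisation balances the strata between arms, so stratum-to-stratum variation in response largely drops out of the observed difference. An unstratified interval still counts that variation in its standard error. If age and vaccination history predict seroconversion or titer ≥1:40, as SAP 8.3 implies, the interval is wider than it needs to be.

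Protocol 8.2 sets no success criteria but says that 95% confidence bounds will be used for statistical comparisons, and Protocol 1.2 says the data will be used to select the dose for Phase 3. At stake are somewhat wider intervals for two of the three derived primary comparisons in Protocol 8.1.1.1, and a slightly lower chance that they exclude zero.

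The move from a commitment to an option has a second effect: under the SAP, the decision to run the adjusted model, and its covariates, could be settled after results are known.

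**Working it through.** **1. The plan's own figure.** Protocol Table 8-1 (SAP Table 3) covers GMT ratios only: 95 per group, SD 0.7, two-sided 5%. The noncentral t distribution with 188 degrees of freedom and noncentrality log10(ratio/bound) / (0.7 × √(2/95)) reproduces all ten entries, for example 83.86% at ratio 2.00 against 1 and 58.44% at ratio 2.50 against 1.5. No rate or power is stated for the binary endpoints.

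**2. Inputs.**
- From the documents: 95 evaluable per arm (Protocol 8.5), equal allocation (Protocol 5.1.4), age split about 50:50 (Synopsis), two-sided 95% intervals.
- Assumed: 50%, 70% or 85% previously vaccinated; true difference d of 15 or 20 points, the same in every stratum; QIVc rates evenly spaced over the four strata across 45–55%, 35–65% or 25–75%, with either factor as the main driver.

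**3. Formulas.** Let stratum k have weight w_k, QIVc rate p0_k and aQIVc rate p1_k = p0_k + d, with arm means P0 and P1.
- Unstratified: V_tot = P0(1−P0) + P1(1−P1)
- Within strata: V_in = Σ w_k [p0_k(1−p0_k) + p1_k(1−p1_k)]
- SE = √(V/95)
- Narrowing = 1 − √(V_in / V_tot)
- Chance that the interval excludes zero = 1 − Φ((1.96 × SE_used − d) / SE_in). Under balanced strata the estimate varies with SE_in, whichever interval is reported.

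**4. Worked case: four equal strata, d = 15 points.** P0 = 0.50 and P1 = 0.65, so V_tot = 0.2500 + 0.2275 = 0.4775, and the half-width is 1.96 × √(0.4775/95) = 13.90 points. For rates 25–75% the between-stratum variance is (0.25² + 0.0833²)/2 = 0.0347 in each arm, so V_in = 0.4775 − 2 × 0.0347 = 0.4081. The other ranges follow the same way.

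| QIVc rates across strata | V_in | Stratified half-width | Narrowing | Chance of excluding zero, unstratified → stratified |
|---|---|---|---|---|
| 45–55% | 0.4747 | 13.86 points | 0.3% | 56.2% → 56.4% |
| 35–65% | 0.4525 | 13.53 points | 2.7% | 56.4% → 58.5% |
| 25–75% | 0.4081 | 12.85 points | 7.6% | 56.7% → 62.9% |

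**5. Range over all the assumptions.** The narrowing is 0.2–0.3%, 1.6–2.8% and 4.4–7.9% for the three ranges. The chance of excluding zero rises by 0.1–0.2, about 1–2 and about 2–6 points. If the strata are not prognostic, V_in = V_tot and both gains are zero.

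**6. Simulation with Miettinen–Nurminen score statistics** (100,000 comparisons per scenario, fixed stratum sizes).

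| QIVc rates across strata | Coverage, unstratified | Rise in chance of excluding zero |
|---|---|---|
| 45–55% | 95.0–95.4% | 0.1–0.3 points |
| 35–65% | 95.6–95.9% | 0.4–2.6 points |
| 25–75% | 96.1–97.0% | 2.5–7.0 points |

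Stratified coverage stays at 94.7–95.3% throughout, including at 85% vaccinated, where each unvaccinated stratum holds about 95 × 0.5 × 0.15 = 7 subjects per arm.

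A separate simulation (200,000 trials per scenario, mean QIVc rate 40%, d = 20 points) varied only the gap between age groups. For gaps of 10, 20, 30 and 40 points, unstratified coverage was 95.6%, 95.9%, 96.5% and 97.2%, and the unstratified interval was 0.5%, 2.2%, 5.0% and 9.5% too wide. Direction and size agree.

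**7. The adjusted model.** The protocol's version is mandatory, but it uses antigen and MF59 levels and does not say that it yields formulation-versus-QIVc differences. The SAP 11.2 version yields those differences but is optional. So no mandatory analysis of the total population is stated to give a strata-adjusted difference for these endpoints.

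**The case against.** The unstratified method is stated consistently in both documents, and SAP 8.1 draws the line openly: GMTs adjusted, main binary analysis not. There is no formal testing, no success criterion and no multiplicity control, and the sample size rests on feasibility. The GMT analysis already adjusts for both factors, and all analyses are repeated by age group (SAP 8.6). The protocol labels its adjusted binary model exploratory and never promised a strata-adjusted difference against QIVc.

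The coverage figures also assume exact balance within strata. SAP 4.1 uses permuted blocks by site and stratum, and with eight arms many blocks may stay incomplete. In a simulation with assumed blocks of eight, 20–40 sites, 70% vaccinated and 5% loss, unstratified coverage was 95.4–95.5% for 35–65% and 95.8–96.3% for 25–75%. That is closer to nominal than under exact balance.

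All of this stands, and it limits the size of the point. It does not remove it. Incomplete blocks reduce the excess coverage, but the stratified interval is still narrower if the strata matter. The by-age tables give no pooled stratified estimate and do not deal with vaccination history. Neither document gives a reason for adjusting the GMTs for both factors while leaving them out of the binary comparisons.

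**Conclusion.** The concern holds as a point of efficiency and consistency. The planned intervals are valid and, if the strata are prognostic, mildly conservative; there is no bias and no inflated error. The loss is negligible when response differs little across strata, about 2–3% of interval width for a 30-point spread, and at most about 8% in the extreme case. These sizes depend on assumed stratum rates, vaccinated shares and true differences, and they are upper-end figures where blocks are incomplete. The mismatch between protocol and SAP on the adjusted model needs no assumption, but it concerns an exploratory analysis and would be minor alone. The change is worth making because it costs almost nothing.

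**What to change.** - In Protocol 8.4.2.2.3 and SAP 8.1 and 11.2, make the Miettinen–Nurminen difference stratified by age group × vaccination history the main analysis of seroconversion and titer ≥1:40. Keep the unstratified interval as supportive.
- In subgroup tables, drop the factor that defines the subgroup, as SAP 8.6 already does for the GMT models by vaccination history.
- State in advance how sparse strata are pooled.
- Give one covariate list for the adjusted binary model. Either restore it to a commitment, as in the protocol, or record the change in SAP 16.
- Separately, reconcile SAP 4.1, which adds site as a stratification factor, with Protocol 5.1.4 and SAP 8.3, which name two factors.

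The cost is wording in two documents and a stratified version of the method already chosen. The one small downside is the need for the pooling rule. No extra subjects or data are required.
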